7.3.4 AE and SAE Reporting Timelines

All **AEs potentially related to thromboembolic events**, whether or not they are suspected to be related to study treatment, are to be reported by telephone, fax, or email to the Clinical Trial Manager.

After the Study Completion Visit, AEs potentially related to thromboembolic events will continue to be monitored proactively by performing a Follow-up Contact 30 days after the completion visit (see **Section 6.1.9**).

All **SAEs**, whether or not they are suspected to be related to study treatment, are to be reported immediately by telephone, fax, or email to the Clinical Trial Manager.

[figure not shown]
CLINICAL TRIAL MANAGER:

[name]

[contact]
[contact]
[contact]
Email: [contact]

The contact details will also be communicated at the study initiation visit.

In addition, within 24 hours after recognition of an SAE, an Octapharma Serious Adverse Event Report must be completed and submitted to:

Waivers the from SAE Reporting Requirement

Waivers from the SAE reporting requirement include surgeries that are elective or were planned before study entry or prolongations of existing hospitalizations for economic or social, but not medical, reasons. Such surgeries or prolongations of hospitalizations should not be considered SAEs.

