6.1.11 Surgical Visits

Patients may undergo surgical interventions in the course of the study. Whether or not patients will be hospitalized will depend on the type and severity of the surgery and be at the discretion of the Investigator.

In patients undergoing major surgeries, standard methods of postsurgical thromboprophylaxis, such as graduated compression stockings and early mobilization, should be used to prevent venous thromboembolism.

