7.2.4 Surgical Prophylaxis Data

The following surgery-related parameters will be documented:

- Body weight within 12 hours before the start of surgery
- Safety laboratory tests (hematology, chemistry) within 12 hours before the start of surgery and 24 hours after the end of surgery (see **Section 7.3.5.2**)
- Vital signs within 12 hours before the start of surgery (before blood sampling)
- Type of surgery (planned or emergency)
- Location of surgery
- Severity of surgery (minor, major) (see definitions under **(a)** below)
- Expected duration of surgery
- Actual duration of surgery (start and end times, i.e., skin to skin)
- Details on IMP dose(s) given pre-, intra-, or postoperatively (see **Section 7.2.1**)
- Pre-, intra-, and postoperative FVIII plasma levels (see definitions under **(b)** below)
- Expected and actual blood loss (see item **(d)** below)
- Presence of wound hematomas and whether or not they require surgical evacuation
- Efficacy assessments at the end of surgery by surgeon (see **Section 7.2.5.1**)
- Efficacy assessment at the end of the postoperative period by hematologist (see **Section 7.2.5.2**)
- Overall efficacy assessment by the Investigator (see **Section 7.2.5.3**)

- Narrative describing the outcome and efficacy of the intervention
- Monitoring of AEs
- Details on concomitantly administered products, including any blood or blood product transfusions but excluding drugs given for routine anesthesia
- Inhibitor testing (see **Section 7.3.5.2**), with a plasma sample obtained within 3–8 weeks after the end of the surgery; this visit can coincide with another study visit with scheduled inhibitor testing.

(a) Severity of surgery

Surgeries are defined as **major** if any of the following criteria are met:

- General or spinal anesthesia required
- Opening into the great body cavities required
- Hemostatic therapy for at least 6 days required
- Orthopedic interventions involving joints (ankle, knee, hip, wrist, elbow, shoulder)
- 3rd molar extraction or extraction of ≥ 3 teeth
- Surgeries/conditions in which the patient's life is at stake

The classification is made prospectively. All other surgeries are classified as **minor**.

(b) Definitions of periods and time points before, during, and after surgery

- **Preoperative** is defined as the time period of up to 3 hours before the start of surgery.
- The **end of surgery** is defined as the time immediately after the last surgical suture.

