7.3.3 Serious Adverse Events (SAEs)

A **serious AE (SAE)** is any untoward medical occurrence that at any dose:

- results in death,
- is life-threatening (see below),
- requires hospitalization or prolongation of existing hospitalization,
- results in persistent or significant disability/incapacity,
- is a congenital anomaly/birth defect,
- is another important medical event (see below).

NOTE: The term ‘**life-threatening**’ refers to an event in which the subject/patient was, in the view of the reporting Investigator, at immediate risk of death at the time of the event; it does not refer to an event which may hypothetically have caused death had it been more severe.

In deciding whether an AE/ADR is serious, medical judgment should be exercised. Thus, important AEs/ADRs that are not immediately life-threatening or do not result in death or hospitalization but may jeopardize the subject/patient or may require intervention to prevent one of the other outcomes listed in the definitions above should also be considered serious.

Examples of ‘**important medical events**’ are all suspected transmissions of an infectious agent, which therefore have to be reported as SAE. A suspected virus transmission means that virus antigen has been detected in the patient. A passive transmission of antibodies alone does not constitute a suspected virus transmission. Another such ‘important medical event’ that has to be reported as an SAE is the development of FVIII inhibitors.

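### The SAE waiver covers any elective surgery, so an on-study event that is serious only through admission for an elective operation may be left out of SAE reporting

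*Protocol*

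**What the plan says.** Protocol section 7.3.3 defines an SAE as an untoward medical occurrence meeting one of a list of criteria. One of these is that it "requires hospitalization or prolongation of existing hospitalization". The section lists no exception for surgery.

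Section 7.3.4 then adds a waiver: "Waivers from the SAE reporting requirement include surgeries that are elective or were planned before study entry". It also waives "prolongations of existing hospitalizations for economic or social, but not medical, reasons", and closes: "Such surgeries or prolongations of hospitalizations should not be considered SAEs".

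Surgery during the trial is foreseen. Section 6.1.11 states: "Patients may undergo surgical interventions in the course of the study". Section 7.2.4 has each operation classified as planned or emergency and counts orthopedic procedures on joints as major surgery. The term *elective* is not defined in either document.

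Protocol 9.2.3 tabulates serious TEAEs and lists patients with SAEs. SAP 5.10.1 gives the incidence of serious TEAEs and a separate listing of SAEs. Neither mentions waived surgeries.

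**The concern.** A waiver for surgery is normally meant to keep operations arranged for old problems out of the safety count. The words *planned before study entry* do that. The word *elective*, joined by *or*, goes further: it covers an operation first decided on during the trial, for a problem that arose or worsened under treatment, provided the operation is scheduled rather than urgent.

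This matters in this population. Section 1.1 describes repeated joint bleeds that lead to severe disability, so a joint that deteriorates during six months of prophylaxis and is then operated on is a plausible event. If a site treats the waiver as settling the matter, the event loses its serious flag, the immediate notification and the 24-hour SAE form. The study is single-arm and is meant to support US approval in hemophilia A (section 1.2), and any omission of this kind can only lower the serious-event count.

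**Working it through.** The plan states no figure on this point, so the check is a side-by-side reading of the rules.

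1. **Scope of the waiver (7.3.4).** The surgery part has two alternatives joined by *or*: elective, or planned before entry. The second is tied to the patient's state before the trial. The first carries no condition on when the need arose, what caused it, or whether the condition worsened on IMP. If only pre-planned surgery had been meant, the first alternative would be unnecessary.

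2. **Contrast within the same sentence.** The waiver for longer stays is confined to non-medical reasons ("prolongations of existing hospitalizations for economic or social, but not medical, reasons"). No such limit is attached to elective surgery.

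3. **What the waiver does.** It goes beyond relaxing a reporting deadline. "Such surgeries or prolongations of hospitalizations should not be considered SAEs" is a statement about classification.

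4. **The rule it meets (7.3.2.2 and 7.3.3).** A pre-existing condition that worsens on study counts as an AE, and an AE that requires hospitalization is an SAE. Take a joint condition that worsens after the first dose and leads to a scheduled hospital operation. Under 7.3.2.2 it is an AE, and under 7.3.3 it is serious through hospitalization. Under 7.3.4 the operation is not to be considered an SAE. If that admission is the only seriousness criterion met, the protocol does not say which section prevails.

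5. **Other routes to a serious flag.** Disability or incapacity remains a criterion. So do important medical events, including those that "may require intervention to prevent one of the other outcomes listed in the definitions above should also be considered serious". Inhibitor development is serious in every case ("that has to be reported as an SAE is the development of FVIII inhibitors"). These routes narrow the gap, but the important-event route rests on the investigator's judgment, whereas hospitalization is an observable fact.

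6. **Whether the analysis recovers the event.** Protocol 9.2.3 and SAP 5.10.1 use the serious flag as recorded. Neither has a rule to reassess waived surgeries.

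7. **Size.** The documents give neither an expected number of elective operations nor an expected number of SAEs, so no undercount can be calculated. For scale only: if all 55 planned patients are in the safety set, one patient whose only serious TEAE went unflagged would shift the incidence by 1/55 = 1.8 percentage points. That is the weight of one patient, not an estimate of how many are affected.

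**The case against.** The strongest reply is that 7.3.4 exempts the surgery and not the condition behind it. Section 7.3.3 defines seriousness by the untoward occurrence, and a natural reading of the waiver is simply that an elective operation is not itself an event. Other sections support this. Under 7.3.2.2 every AE is documented and the investigator grades its seriousness. Under 7.3.2.1 an AE that leads to an intervention can be classed as another significant AE. AEs possibly related to thromboembolism go to the Clinical Trial Manager whatever the waiver says (7.3.4). All TEAEs are tabulated, and operations treated with Wilate are documented and reported separately (7.2.4, SAP 5.9), so a reader could cross-check.

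Much of this stands. A reader might infer that every condition arising on study and treated by elective surgery drops out of the SAE count. The documents do not support that: the condition stays in the AE and TEAE data, and it may be flagged serious by another criterion or by an investigator who reads the waiver narrowly. Nor do they show how often a planned admission would be the only criterion met. *Elective* also cannot simply be equated with the *planned* category of 7.2.4, because nothing links the two.

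What the reply does not supply is an instruction. Nowhere is the investigator told that the underlying event must still be judged against the hospitalization criterion when the operation is waived. Two sites could follow the text in good faith and classify the same event differently.

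**Conclusion.** The concern holds as a gap in a reporting rule. The elective part of the waiver is not restricted to pre-existing, unworsened conditions, and 7.3.4 does not preserve the assessment under 7.3.3. An event whose only seriousness criterion is admission for an elective operation may therefore be left out of SAE reporting and the serious-TEAE outputs. At most its serious flag and expedited report are lost; the AE record is not. The size cannot be estimated from the documents, and any percentage would rest on invented event counts.

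This rests on the supplied protocol, version 03 of 16-Jan-2017. SAP section 1 cites a protocol dated 2017-09-07 that includes Amendment #04, which was not available, so it should be confirmed that the waiver was unchanged there. The point merits a wording change. It is not evidence that serious events were in fact missed.

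**What to change.** Reconcile 7.3.4 with 7.3.3:

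- Limit the surgery waiver to elective or pre-planned surgery for a condition that was present before study entry and has not worsened since the first dose of IMP.
- State that any AE with onset or worsening on study that leads to hospital admission for surgery, elective or emergency, is assessed for seriousness under 7.3.3.
- Define *elective* and say how it relates to the planned/emergency item in 7.2.4.

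The waiver should not be extended to emergency surgery. A version resting only on the condition being pre-existing, whatever the urgency of the operation, would newly exempt unplanned emergency procedures, so the elective or pre-planned requirement has to stay.

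This changes safety reporting only and leaves patient care as it is. It needs a short protocol amendment and a note to sites. The downside is a few more SAE forms and possibly a slightly higher serious-TEAE count.

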7.3.5 Laboratory Tests

The following laboratory parameters will be determined at the time points specified in the flow charts of assessments on **pages 16 and 18** and in **Section 6**.

7.3.5.1 Central Laboratory

The following laboratory tests will be done at the central laboratory:

- **FVIII:C** in the vials used for PK injections as well as in plasma using the CHR and OS assays
- **FVIII inhibitor activity** will be determined at each study visit before the injection of *Wilate* using the modified Bethesda assay (Nijmegen modification). Blood sampling for inhibitor testing should preferably be performed at the time of trough FVIII:C levels.

If inhibitor development is suspected between study visits (e.g., based on an unexplained need to increase the dose, lack of efficacy of IMP injections, or prolonged bleeding) (see also **Section 6.1.9**), additional FVIII inhibitor tests will be performed and documented.

In case of positive inhibitor results, inhibitor retesting using a second, separately drawn sample should be performed, preferably within 15 days of becoming aware of the positive result. If inhibitor development is confirmed by the second sample analyzed in the central laboratory, patients with low-titer inhibitors (<5 BU) may continue treatment with *Wilate*, while patients with high-titer inhibitors will be discontinued from the study.

- **VWF:Ag** and **VWF:Ac** will be measured at prespecified time points.
VWF:Ac will be measured by INNOVANCE[®] VWF Ac (Siemens Healthcare Diagnostics), which is a particle enhanced assay for the automated determination of VWF activity in human citrated plasma. The assay principle makes use of the binding of VWF to its receptor Glycoprotein Ib (GPIb). GPIb is the main VWF receptor on platelets. Polystyrene particles are coated with an antibody against GPIb. Recombinant GPIb (two gain-of-function mutations included) is added and binds to the antibody as well as to the VWF of the sample. Due to the gain-of-function mutations, VWF binding to GPIb does not require ristocetin. This VWF binding induces a particle agglutination which can be measured as an increase in extinction by turbidimetric measurements.
- **Virus safety** will be evaluated by taking a plasma sample for parvovirus B19 antibody testing before the first injection of *Wilate*. All patients negative at baseline will be tested again at the Study Completion Visit.

A retention serum sample for possible virus marker testing will also be taken before the first injection of *Wilate* and stored at the central laboratory.

Central laboratory:

SYNLAB pharma institute

[name]
[name]
Germany

7.3.5.2 Local Laboratory

The following laboratory tests will be done by the local laboratories of each study site:

- **Hematology:** red blood cell count, white blood cell count, hemoglobin, hematocrit, and platelet count
- **Chemistry:** total bilirubin, alanine amino transferase, aspartate transaminase, blood urea nitrogen, serum creatinine

CD4+ and **AB0 blood-type testing** as well as **FVIII:C measurements in case of surgery** will also be done by the local laboratories. Samples for surgery-related FVIII:C testing will also be shipped to the central laboratory for OS and CHR assay assessments.

The methods of determination and normal ranges for each parameter will be provided in the clinical study report.

7.3.6 Vital Signs and Physical Examination

The vital signs obtained at the time points specified in **Section 6** are blood pressure, body temperature, heart rate, and respiratory rate.

Physical examinations will be performed at the visits specified in **Section 6**. Both height and weight will be measured at baseline. In addition, weight will be measured at all visits prior to dosing.

7.3.7 Other Relevant Safety Information

(a) Post-study related safety reports

After the Study Completion Visit, any AEs potentially related to thromboembolic events will continue to be monitored proactively by performing a Follow-up Contact 30 days after the completion visit (see **Sections 6.1.9** and **7.3.4**).

In addition, any **SAE** which occurs up to 4 weeks after the last IMP administration should be reported by the Investigator to the Sponsor in case the Investigator becomes aware of it. Proactive monitoring for post-study SAEs is not required.

If any such post-study event is identified, the Investigator will complete an SAE form and transmit it to the Clinical Trial Manager (see **Section 7.3.4**).

Deaths occurring within 4 weeks after the last IMP administration should also be reported, regardless of whether or not they are considered treatment-related.

Overdose, interaction, medication error

The following safety relevant information should be reported as AE or, if the reaction fulfils one of the criteria for seriousness, as SAE.

(b) Drug overdose

An overdose is a deliberate or inadvertent administration of a treatment at a dose higher than specified in the protocol and higher than the known therapeutic dose that is of clinical relevance. The reaction must be clearly identified as an overdose.

(c) Drug interaction

A drug interaction is a situation in which a substance or medicinal product affects the activity of an IMP, i.e., increases or decreases its effects, or produces an effect that none of the products would exhibit on its own. The reaction must be clearly identified as a drug interaction.

(d) Medication error

A medication error involves the inadvertent administration or unintended use of a medicinal product which may be caused by the naming, presentation of pharmaceutical form/packaging, or instructions for use/labelling. The reaction must be clearly identified as a medication error.

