- [5] Blood sampling within 1 h before injection and 15 ± 5 min, 1 h (± 5 min), 3 h (± 15 min), 6 h (± 30 min), 9 ± 1 h, 24 ± 2 h, 30 ± 2 h, and 48 ± 2 h after end of injection **[central laboratory]**
- [6] Blood sampling within 1 h before injection as well as 15 ± 5 min after the end of injection **[central laboratory]**
- [7] If first sample was negative for parvovirus B19 antibodies (sample to be taken before injection) **[central laboratory]**
- [8] CD4+ count to be repeated if interval between Screening Visit and first injection exceeds 30 days. To be included into the study, the patient's CD4+ count must be $>200/\mu\text{L}$ (i.e., inclusion criterion no. 4).
- [9] Unless obtainable from patient's medical history
- [10] First prophylactic injection
- [11] Blood sampling for inhibitor testing should preferably be done at the time of trough FVIII:C levels **[central laboratory]**
In case of positive inhibitor results, inhibitor retesting using a second, separately drawn sample should be performed, preferably within 15 days of becoming aware of the positive result.
- [12] Documentation of AEs potentially related to thromboembolic events only

FLOW CHART OF ASSESSMENTS FOR SURGICAL PROPHYLAXIS

	For details, see Section	Within 12 hours before start	Within 3 hours before start	Surgery		POP day 1	Any POP day	End of POP period	3-8 weeks after surgery
				Intra-operatively	End [1]				
Body weight		x							
Type of surgery		x							
Location of surgery		x							
Severity of surgery	7.2.4	x							
Expected duration of surgery		x							
Expected average/ maximum blood loss during surgery	7.2.4	x							
Actual duration of surgery					x				
Actual blood loss during surgery					x				
Administration of IMP			x	(x)	(x)	(x)	(x)	(x)	
FVIII plasma levels	7.2.4		#	(#)	(#)	# [2]	#	#	
VWF:Ag and VWF:Ac	7.3.5		#			# [2]	#	#	
Presence of wound hematomas						x	x	x	
Routine safety laboratory	7.3.5	x				(x)	(x)	(x)	
Vital signs	7.3.6	x		x		x			
Efficacy assessment	7.2.5				S			H	
Overall efficacy assessment	7.2.5							I	
Factor VIII inhibitor [3]	7.3.5								x
Narrative of outcome								x	
Concomitant medications		throughout observation period							
Adverse event monitoring	7.3	throughout observation period							

POP = postoperative, VWF:Ag = von Willebrand factor antigen, VWF:Ac = VWF activity

() Optional

Samples to be taken immediately before (≤ 30 min) and 30 \pm 15 min after IMP administration

[1] Time immediately after the last surgical suture

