6.1.9 Follow-up Contact 30 days after Study Completion Visit

The purpose of the Follow-up Contact 30 days after the 6-month Study Completion Visit is to **document any AEs potentially related to thromboembolic events**, whether or not they are suspected to be related to study treatment.

The Follow-up Contact may take either the form of a personal visit by the patient to the study site or a telephone call by the Investigator. Any relevant AEs are to be recorded on the AE page of the eCRF.

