7.3.2.6 Outcome of AEs

The outcome of all reported AEs has to be documented as follows:

1. Recovered, resolved
2. Recovering, resolving
3. Not recovered, not resolved
4. Recovered, resolved with sequelae
5. Fatal
6. Unknown

NOTE: A patient's **death** per se is not an event, but an outcome. The event which resulted in the patient's death must be fully documented and reported, even in case the death occurs within 4 weeks after IMP treatment end and regardless of whether or not it is considered treatment-related.

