2.4 Study design

This study is designed as a prospective, international, multi-center phase 3 study. Further details are given in the overview below:

FLOW CHART FOR PK ASSESSMENT AND PROPHYLACTIC TREATMENT

Part I

	Screening Visit	PK Patients	Non-PK Patients	Day-14 Visit (14-21 days)	Day-30 Visit (±3 days)	3-Month Visit (±2 weeks)
		PK Visit	Non-PK Visit			
Informed consent	x					
Inclusion and exclusion criteria	x					
Demographics	x					
Weight	x	x [1]	x [1]			x [1]
Height	x					
Medical history (incl. FVIII treatment 6 months before screening)	x					
Vital signs	x	x [2]	x [4]			x [4]
Physical examination	x					
Routine safety laboratory	x	x [3]	x [4]			x [1]
Determination of CD4+ levels [8]	x					
Determination of AB0 blood group [9]	x					
HJHS, unless obtained within 3 months before screening	x					
PK injection (50 ± 5 IU/kg)		x				
Blood sampling for FVIII:C (OS and CHR) for PK assessment		x [5]				
IVR injection			x [10]			x
Blood sampling for FVIII:C IVR (OS and CHR)			x [6]			x [6]
Factor VIII inhibitor [11]	x	x [1]	x [1]	x [1]	x [1]	x [1]
VWF:Ag and VWF:Ac		x [6]	x [6]	x [1]	x [1]	x [6]
Parvovirus B19 antibodies		x [1]	x [1]			
Retention sample for possible virus marker testing		x [1]	x [1]			
Patient diary review				x	x	x
Adverse event monitoring		x	x	»	»	»
Concomitant medications	x	»	»	»	»	»

PK = pharmacokinetic, IVR = in vivo recovery, HJHS = Hemophilia Joint Health Score, OS = one-stage assay, CHR = chromogenic assay, VWF:Ag = von Willebrand factor antigen, VWF:Ac = VWF activity

<h2 style="margin: 0;">STATISTICAL ANALYSIS PLAN</h2> <h3 style="margin: 0;">Protocol No: WIL-27</h3>	
Version Number: 5.0 Date of Issue: 2018-05-08	Page 12 of 27

Part II

	PK Patients	Non-PK Patients	
	PK Study Completion Visit at 6 months (+2 weeks)	Non-PK Study Completion Visit at 6 months (+2 weeks)	Follow-up Contact 30 days (±3 days) after Study Completion Visit
Informed consent			
Inclusion and exclusion criteria			
Demographics			
Weight	x [1]	x [1]	
Height			
Medical history (incl. FVIII treatment 6 months before screening)			
Vital signs	x [2]	x [4]	
Physical examination	x	x	
Routine safety laboratory	x [3]	x [4]	
Determination of CD4+ levels [8]			
Determination of AB0 blood group [9]			
HJHS, unless obtained within 3 months before screening			
PK injection (50 ± 5 IU/kg)	x		
Blood sampling for FVIII:C (OS and CHR) for PK assessment	x [5]		
IVR injection		x	
Blood sampling for FVIII:C IVR (OS and CHR)		x [6]	
Factor VIII inhibitor [11]	x [1]	x [1]	

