8 APPENDICES

8.1 Formulas for derived variables

Variable	Description
Durations between two dates	Later date minus earlier date plus 1, expressed in days. (Remark: Duration will be 1, if both dates are the same.)
Annual bleeding rate	Number of bleedings under prophylaxis / time under prophylaxis (days)/365.25 (see prophylactic treatment phase)
AUC	Area under the curve from baseline to infinity $AUC = \sum \left(\frac{(C_n + C_{n+1})}{2} \cdot \Delta t \right) + \frac{C_{last}}{K}$ (C_{last} is the last available measurement)
AUC _{norm}	AUC normalized for the administered dose
AUMC	Area under the moment curve (from baseline to infinity) $AUMC = \sum \left(\frac{(t_n \cdot C_n + t_{n+1} \cdot C_{n+1})}{2} \cdot \Delta t \right) + \frac{C_{last}}{K^2} + \frac{t_{last} \cdot C_{last}}{K}$
CL	Clearance $CL = \frac{D}{AUC}$ where D is the actual dose administered (see remark above)
C_0	FVIII concentration before IMP administration
C_{max}	Maximal measured concentration after end of IMP infusion (peak concentration)
ED	Exposure day = each day the subject received IMP
Incremental recovery (IVR)	$IVR = \frac{(C_{max} - C_0) \cdot BW}{D}$

STATISTICAL ANALYSIS PLAN

Protocol No: WIL-27

Version Number: 5.0

Date of Issue: 2018-05-08

Page 26 of 27

	where BW stands for the body weight in kg and D is the dose according to the actual potency of the FVIII concentrate as described in above
MRT	Mean residence time $MRT = \frac{AUMC}{AUC}$
Prophylactic treatment phase	PK subgroup: (date of completion visit or date of last treatment with IMP in case completion visit not performed) – (date of first prophylactic treatment after the PK visit) Non-PK subgroup: (date of completion visit or date of last treatment with IMP in case completion visit not performed) – (date of first IMP infusion at Non-PK visit)
Success (for bleeding episodes and surgeries)	Excellent or good efficacy rating
T _{1/2}	In vivo half-life using linear regression on the terminal phase of the logarithm of the concentration; $T_{1/2} = \frac{\ln(2)}{K}$ (where K, the elimination rate constant, is determined as the slope of the regression line)
T _{max}	Time to reach maximum plasma concentration (Timing starts at end of infusion)
Vd	Volume of distribution $Vd = CL \cdot MRT$

STATISTICAL ANALYSIS PLAN Protocol No: WIL-27	
Version Number: 5.0 Date of Issue: 2018-05-08	Page 27 of 27

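### The 30-day Follow-up Contact asks only about thromboembolic events and is dated from the Completion Visit, so other reportable SAEs after the last dose are not actively sought, and withdrawn patients who skip that visit have no contact date

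*Protocol*

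**What the plan says.** **What is reportable.** Protocol 7.3.7 asks the investigator to report any SAE "which occurs up to 4 weeks after the last IMP administration", on condition that it comes to the investigator's attention, and then says: "Proactive monitoring for post-study SAEs is not required". The same section makes deaths in those 4 weeks reportable without that condition. Section 7.3.2.6 says that the event behind a death "must be fully documented and reported, even in case the death occurs within 4 weeks after IMP treatment end". Neither section says how such a death is to be found.

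**What the site does after the last visit.** Section 6.1.9 describes "The purpose of the Follow-up Contact 30 days after the 6-month Study Completion Visit" as recording AEs that may be thromboembolic. It may be a visit or a telephone call. Note [12] to the protocol flow chart reads: "Documentation of AEs potentially related to thromboembolic events only". The SAP repeats that note under its own flow chart (Section 2.4), which heads the column "Follow-up Contact 30 days (±3 days) after Study Completion Visit". SAP 5.10.1 lists post-study SAEs and states that they are not proactively monitored.

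**Withdrawn patients.** Protocol 6.1.7 and 6.1.8 ask patients who leave early to come to the Completion Visit but do not make attendance a requirement. SAP 8.1 allows for the visit being missed: it ends the prophylactic phase at the "date of last treatment with IMP in case completion visit not performed". Neither document gives a substitute date for the Follow-up Contact.

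**The concern.** The protocol sets a 4-week reporting window and schedules a contact at about the time that window closes, but does not use the contact to ask about the events that the window covers. The TEAE definition (protocol 7.3.2.1 and 9.2.3, SAP 5.10.1) has a start and no end, so an SAE that begins after the last dose belongs in the serious-TEAE tables as well as in the listing. Whether it gets there depends on someone volunteering it. An absence of entries for this period could not be read as an absence of events.

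The anchor date raises a second, separate problem. Sections 7.3.4 and 7.3.7 call the thromboembolic follow-up proactive. For a withdrawn patient with no Completion Visit it has no due date, and patients who stopped because of an AE may be among them.

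**Working it through.** The plan gives no figure on this point, so there is none to reproduce. The check compares dates and content, followed by an illustration of size.

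**1. Timing for completers.** Sections 6.1.7 and 6.1.8 have IMP given at the Completion Visit. The SAE and death window is 4 weeks = 28 days from the last dose. The contact is at day 30, or day 27 to 33 with the SAP's tolerance.

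- Nominal: 30 − 28 = 2 days after the window closes.
- Latest: 33 − 28 = 5 days after it closes.
- Earliest: 27 − 28 = −1, so one day of the window is still to run.

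Apart from that one day, the contact is already late enough to cover the window. For completers the main limit is its content.

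**2. Timing for withdrawn patients.** If the last dose was g days before an attended Completion Visit, the contact falls g + 30 days after that dose.

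| g (days) | Nominal contact day after last dose | Range with ±3 days |
|---|---|---|
| 7 | 37 | 34–40 |
| 14 | 44 | 41–47 |
| 28 | 58 | 55–61 |

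If there was no Completion Visit, the formula has no starting point and the contact date is undefined.

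**3. Content.**

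- Thromboembolic AEs, serious or not: actively sought at the contact.
- Deaths: reporting is required, with no stated way of finding them. A call would probably reveal a death, but only where a call is due.
- All other new SAEs: reported only if they come to the investigator's notice.
- AEs already open when the patient leaves: followed until resolved or stable (7.3.2.1 and 7.3.2.7), so not part of the gap.

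**4. Size, as an illustration only.** The documents give no SAE rate. Assume an annual SAE risk r and a constant hazard. The 28-day risk is p = 1 − (1 − r)^(28/365.25). With 55 patients, the expected number with an SAE is 55p, and the chance of at least one is 1 − (1 − p)^55.

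| Assumed r | p | 55p | Chance of at least one |
|---|---|---|---|
| 2% | 0.00155 | 0.09 | 8% |
| 5% | 0.00392 | 0.22 | 19% |
| 10% | 0.00804 | 0.44 | 36% |
| 20% | 0.01696 | 0.93 | 61% |

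These are patients with an event in the window, not patients missed. The number missed is smaller, because some events are volunteered and thromboembolic ones are asked about. For scale, one patient is 1/55 = 1.8 percentage points of a subject incidence in the safety set, if all 55 are treated.

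**The case against.** The strongest reply is that this is a declared choice. Protocol and SAP agree, and the SAP labels these SAEs openly as not actively monitored. The condition on the investigator's awareness applies to SAEs and not to deaths, so 7.3.7 does not contradict 7.3.2.6. That is correct: the point is a gap in design, not an inconsistency.

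A second reply is that Section 7.3.2.2 already requires a non-leading AE question at every visit, and that any SAE mentioned at the contact makes the investigator aware of it. This helps in part. However, the contact may be a telephone call, and note [12] confines what is documented to thromboembolic AEs.

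A reader might infer more than the documents support:

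- **That every SAE and death after the last dose is found only by chance.** Thromboembolic SAEs are actively sought, and a death would probably emerge when a site calls. PK patients also have safety laboratory tests and vital signs 48 hours after the final PK dose.
- **That the contact would detect inhibitors or virus transmission.** Section 7.3.3 classes both as SAEs, but inhibitors are found by assay and a suspected transmission requires detected virus antigen. A question can at most bring out symptoms or results obtained elsewhere.
- **That a known share of SAEs is lost.** Any such percentage merely restates an assumed volunteering rate.
- **That up to 5 of 55 patients lack a contact date.** The 5 are the margin for reaching 50 completers. They are neither a count of missed Completion Visits nor an upper limit on it.

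One limit remains. SAP Section 1 relies on a protocol dated 2017-09-07, later than the version reviewed here, so a revised anchor date cannot be excluded. The SAP itself still carries the thromboembolic-only note and the passive SAE collection.

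**Conclusion.** The point holds in a limited form. New non-thromboembolic SAEs in the 28 days after the last dose are reportable but not actively sought, although a contact at nearly the right time is already planned. A withdrawn patient without a Completion Visit has no defined contact date, even for the thromboembolic follow-up; how many such patients there would be is not stated. The serious-TEAE tables and the post-study SAE listing may therefore be incomplete for this period.

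The expected size is small: about 0.1 to 0.9 patients with an SAE in the window among 55, if the annual SAE risk is 2% to 20%, the hazard is constant and all 55 are treated. The TABR analysis is unaffected. The change is worth making because it is cheap and because, in a study of this size, a single unreported serious event is visible in the incidence.

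**What to change.** Amend protocol 6.1.9, 7.3.4, 7.3.7 and flow-chart note [12], together with the matching SAP note and SAP 5.10.1, as follows:

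1. At the existing Follow-up Contact, ask the non-leading AE question of 7.3.2.2. Record all SAEs and deaths as well as thromboembolic AEs.
2. Remove the 7.3.7 sentence that waives proactive monitoring, at least for the 4-week window, and the corresponding remark in SAP 5.10.1.
3. Date the contact 30 days after the last IMP dose for every treated patient, whether or not a Completion Visit took place.
4. Keep the SAP's tolerance but set a floor at day 28, so that the permitted range becomes day 28 to 33 after the last dose.

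No new visit or sample is needed. The cost is protocol and SAP wording, one more question in a contact already planned, a few more SAE reports, and calls to withdrawn patients who did not attend the Completion Visit.
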